**Table 1. Visit Windows in Part 2**

Analysis Visit	Study Day	Analysis Window
Week 18	126	$123 \leq \text{Study Day} \leq 132$
Week 20	140	$133 \leq \text{Study Day} \leq 147$
Week 22	154	$148 \leq \text{Study Day} \leq 161$
Week 24	168	$162 \leq \text{Study Day} \leq 182$
Week 32	224	$210 \leq \text{Study Day} \leq 238$
Week 56 and every 24 weeks thereafter	392, every 168 days thereafter	$\text{Study Day} - 14 \text{ days} \leq \text{Study Day} \leq \text{Study Day} + 14 \text{ days}$

Records from unscheduled or end of treatment visits that do not fall within an analysis window will be listed, but will not be analyzed. For the 6MWT analysis, if use of the visit windows yields more than one value for a particular visit, the average of the two or more values will be used for analysis. For all other analyses, including the eGFR and safety analyses, the value closest to the target study day should be used. Visits that do not occur in all versions of the protocol (i.e., Part 2 visits past week 32 that were changed to phone visits) should be treated as unscheduled assessments.

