All patients in Part 1 of the study (i.e., Cohorts 1, 2, 3a-b, and 4a-d) will follow similar visit and assessments schedules. Selected assessments () will be optional for all enrolled patients at Sponsor-qualified sites. Other assessments (e.g., ABPM,) conducted for Cohorts 1 and 2 will not be conducted for patients in Cohorts 3 and 4. Following randomization, patients will be assessed in person during treatment at Weeks 1, 2, 4, 8, 12, and 16 and by telephone contact on Days 3, 10, and 21. Patients enrolling in Cohorts 3 and 4 will have additional assessments in person at Week 6 and additional telephone contact on Days 31, 38, and 49. Patients who do not enter Part 2 of the study (i.e., the extension period), either because they have discontinued taking study drug during Part 1 or have completed the 16-week treatment period as planned but chosen not to continue to Part 2 of the study, will complete an end-of-treatment visit when patient ends study drug. In addition a follow-up visit should occur four weeks after the date of administration of the last dose of study drug.

Part 2 (extension period):

Patients who discontinue treatment prematurely in study Part 1 are not eligible to continue into study Part 2. All patients from Part 1 who complete the 16-week treatment period as planned will be eligible to continue directly into the extension period to evaluate the intermediate and long-term safety and efficacy of bardoxolone methyl. Day 1 of the extension period will be the same as the Week 16 visit for the treatment period.

Cohort 1 and Cohort 2 patients randomized to placebo in Part 1 of the study will be assigned to receive bardoxolone methyl at their group-specific dose in the extension period. Patients enrolled in Cohorts 1 and 2 may dose titrate to the 10 mg dose or de-escalate at scheduled or unscheduled visits. However, patients who dose escalate must have a telephone call 1 week after

dose escalation and an unscheduled office visit or a home health visit 2 weeks (± 3 days) after dose escalation to collect clinical chemistry, BNP, and NT-Pro BNP.

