Cohorts 3 and 4 patients randomized to placebo in study Part 1 will be assigned to 5 mg of bardoxolone methyl, whereas, patients randomized to bardoxolone methyl in study Part 1 will begin study Part 2 (Week 16) at the same dose of bardoxolone methyl as they ended with in study Part 1. All patients in Cohorts 3 and 4 will have the option to up-titrate their dose at the Week 20 visit, and may de-escalate in dose (minimum dose of 2.5 mg) at scheduled or unscheduled visits. Treatment assignment will remain blinded for Cohort 3 and 4 patients through Week 20.

Treatment-compliant patients who have completed Part 2 of the study are eligible to continue receiving bardoxolone methyl through an extended access program (Study 402-C-1602). After Week 32, visits will occur every 24 weeks until bardoxolone methyl is available through the extended access program. Once bardoxolone methyl is available through the extended access program, patients in Part 2 who have completed at least 32 weeks of the study will complete an End of Treatment Visit. The Week 32 visit may be the same as the End of Treatment Visit. Beginning with the Week 32 visit, patients will be seen in the clinic every 24 weeks (i.e., Week 56, Week 80, Week 104, etc.) and receive a 6-month supply of study drug at the appropriate dose.

The Sponsor reserves the right to stop the study for a given cohort if development of bardoxolone methyl is discontinued for any reason, or if the assessment of available data raises concerns about the safety or efficacy of bardoxolone methyl.

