Clinical chemistry ^j			X		X	X	X	X	X
BNP and NT-Pro BNP ^{l,k}			X		X	X	X ^k	X ^k	X
Hematology			X		X	X	X	X	X
Urinalysis and microscopy			X		X	X	X	X	X
6-min walk test					X	X	X	X	X
██████████					█	█	█	█	█
██████████						█		█	
Functional class assessment ^m						X		X	X
PK samples ⁿ					X				

^a All other Week 16 assessments will be completed as per Table 3 or Table 4.

^b Under delegation of the Investigator and with prior Sponsor approval, a patient may be seen by a home health professional. The home health professional must have documented study-specific training on file prior to the performance of any study-related procedures.

^c Visits beyond Week 32 will only occur until bardoxolone methyl is available through the extended access program. Once bardoxolone methyl is available through the extended access program, patients in Part 2 who have completed at least 32 weeks of the study will complete an End of Treatment Visit. If bardoxolone methyl is available through the extended access program prior to Week 32, the End of Treatment visit may coincide with the Week 32 visit.

^d Patients who are discontinued from the study during the extension period for any reason, including Sponsor termination of the study, and patients who are not participating in the extended access program must complete all end-of-treatment and follow-up visit assessments. Patients should complete the end-of-treatment assessments, including the 6MWT, prior to any adjustments being made to their PAH-specific treatment regimen.

- ^e Weights taken at home by the patient should be taken daily starting at week 16 through and including week 20 and weekly thereafter, preferably at the same time each day and must be recorded in a diary and reviewed with the coordinator during telephone contacts and office visits.
- ^f If clinical worsening is suspected, further clinical evaluations may be required per Section 9.10.32.
- ^g A limited physical assessment directed to assess for fluid retention and clinical worsening may be performed by a home health professional under the delegation of the Investigator
- ^h A serum pregnancy test will be performed at Screen A for WOCBP or at any point in time if a pregnancy is suspected. All other pregnancy assessments will be urine pregnancy tests. Additional pregnancy assessments will be performed more frequently if required by local law or requested by local regulatory authorities or IRBs/ECs.

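### Part 2 analysis windows leave 139 of every 168 days after Week 32 uncovered, so end-of-treatment values taken off the visit grid drop out of the by-visit summaries

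*SAP*

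**What the plan says.** SAP 3.7.3 admits a Part 2 assessment to the efficacy and safety analyses only if it falls in a Table 1 window. Those windows are Days 123-132, 133-147, 148-161 and 162-182 (Weeks 18 to 24), Days 210-238 (Week 32), and 14 days either side of Day 392 and of every 168th day after it. For anything else, the text under Table 1 reads: "Records from unscheduled or end of treatment visits that do not fall within an analysis window will be listed, but will not be analyzed". SAP 3.4.5 likewise keeps safety results outside a window out of the table summaries. SAP 3.5.5 carries the Part 1 safety methods into Part 2 and counts adverse events by onset or worsening after Week 16, not by visit.

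The end-of-treatment visit has no fixed day. Under footnote d of Protocol Tables 5 and 6, patients who are discontinued during the extension for any reason, or who do not enter the access program, "must complete all end-of-treatment and follow-up visit assessments". Protocol 7.1 adds that once that program is open, "patients in Part 2 who have completed at least 32 weeks of the study will complete an End of Treatment Visit". Otherwise, clinic visits after Week 32 are 24 weeks apart.

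Part 1 is handled differently. SAP 3.4.4, 3.4.5 and 3.7.2 assign the end-of-treatment value of a patient who stops before Week 16 to the nearest nominal visit, and the Table 2 windows run without a gap to Day 119.

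**The concern.** Scheduled Part 2 visits sit comfortably inside their windows, which makes Table 1 look harmless. The end-of-treatment visit is the exception: its date is set by the patient's decision to stop or by the opening of the access program. A wholly off-grid visit after Week 32 is more likely than not to miss a window. It would then contribute nothing to the tabulated laboratory values, vital signs, eGFR, ECG or 6MWD.

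These are the last values for each patient, including those who stopped because something went wrong. Part 2 is meant to describe intermediate and long-term safety and efficacy (Protocol 7.1), and its results may go into regulatory interactions (SAP 1.9.4). ECG is the sharpest case. In Protocol Tables 5 and 6, the only ECGs scheduled after Week 32 are at end of treatment and follow-up, and Table 1 has a row for neither.

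**Working it through.** **Inputs.** Windows and target days come from SAP Table 1. Visit tolerances (3 days through Week 24, 5 days from Week 32) come from Protocol Tables 5 and 6. Part 2 is counted from Day 113, the day after the Week 16 target.

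**1. Reproduce the target days.** Day = 7 x week gives 126, 140, 154, 168, 224 and 392 for Weeks 18, 20, 22, 24, 32 and 56, and 24 x 7 = 168 for the later cycle. All match Table 1.

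**2. Count the gaps.**
- Days 183-209: 27 days.
- Days 239-377: 139 days.
- Days 407-545, and the same stretch in each later cycle: 139 days.
- Days 113-122 also precede the first Table 1 window: 10 days.

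**3. Uncovered share.**

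| Span | Days | Covered | Uncovered |
|---|---|---|---|
| 113-224 (to Week 32) | 112 | 60 + 15 = 75 | 37 (33.0%) |
| 113-392 (to Week 56) | 280 | 60 + 29 + 15 = 104 | 176 (62.9%) |
| 225-392 (one cycle after Week 32) | 168 | 14 + 15 = 29 | 139 (82.7%) |

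The 60 is the unbroken run of Days 123-182. Uncovered days first become the majority when follow-up reaches Day 291 (Week 41.6): 90 of 179 days.

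**4. End-of-treatment visits after Week 32.** A visit held at Week 32 (Days 219-229) or Week 56 (Days 387-397) lies wholly inside its window, so none is lost. If a fraction f of visits is instead spread evenly over the cycle, the share lost is f x 139/168:
- f = 0: 0%
- f = 0.5: 41.4%
- f = 1: 82.7%

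The documents do not give f. If stops before Week 32 are spread evenly over Days 113-224, the corresponding share is 33.0%.

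**5. Post-escalation checks.** Cohorts 3 and 4 may up-titrate at Week 20. Their Week 22 visit (Days 151-157) and Week 24 visit (Days 165-171) are fully inside windows. For Cohorts 1 and 2, Protocol 7.1 requires a telephone call one week after "dose escalation and an unscheduled office visit or a home health visit 2 weeks" later, give or take 3 days:
- Escalation on the Week 16, 18 or 20 target day puts the check on Days 123-129, 137-143 or 151-157. All 7 possible days are inside.
- Escalation on the Week 32 target day puts it on Days 235-241, of which 4 of 7 are inside. Week 56 gives the same result. Allowing the 5-day visit tolerance as well, 42 of 77 combinations (6 of 11) are inside.
- Escalation on evenly spread unscheduled days over Days 225-392 (an assumption) leaves 82.7% outside.

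**The case against.** The best defence is that little of consequence is lost.
- Adverse events are counted by date, up to 30 days after the last dose (SAP 3.4.5.1). Protocol 11.3 and 11.6 require clinically significant laboratory and ECG changes to be recorded as adverse events.
- Concomitant medication and exposure summaries follow medication and dose dates. All data appear in by-patient listings (SAP 2.3).
- Part 2 has no concurrent placebo and no inferential statistics (SAP 3.5.4).
- Patients receive a 6-month supply at 24-week visits, and the end-of-treatment visit may coincide with Week 32 (Protocol 7.1). Many could therefore fall inside a window.
- Some analysis text is redacted, and further detail is left to mock tables that are not public.

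All of this stands, and it limits the point to by-visit descriptive tables. It does not fill the gap. A listing is not a summary, and adverse event tables do not show the distribution of last laboratory, ECG or walk values. SAP 3.4.5 also assigns unscheduled safety results to the closest nominal visit, but its next rule, like 3.7.3, leaves out-of-window results in listings only.

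A reader might infer that post-escalation checks are mostly lost. Step 5 shows otherwise: they are fully retained in Cohorts 3 and 4, and mostly retained in Cohorts 1 and 2 when escalation happens on the target day of a scheduled visit. Only off-grid escalation in Cohorts 1 and 2 after Week 32 would be mostly lost, and the protocol contradicts itself on whether that can happen. Section 7.1 allows it at scheduled or unscheduled visits. Section 7.3 says those cohorts have no intra-patient escalation, and later limits extension-period escalation to Week 20 for all patients.

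**Conclusion.** The point holds for the by-visit laboratory, vital-sign, eGFR, ECG and 6MWD summaries in Part 2. After Week 32, 83% of days lie outside any window. The share of end-of-treatment visits lost there runs from 0% (all at scheduled visits) to about 83% (evenly spread), and the documents give no timing to narrow that range. The contrast with Part 1, where premature end-of-treatment values are kept, rests on the visible text.

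Three stronger readings are not supported:
- These visits do not vanish from every summary, because adverse event, concomitant medication and exposure summaries are not windowed.
- Most of Part 2 is not uncovered from the outset: 67% of days are covered to Week 32 (75 of 112), and uncovered days become the majority only at about Week 42.
- The tables have not been shown to look safer than the data. That direction is plausible for patients who stop because of harm, but end-of-treatment visits also include administrative transfers to extended access, whose omission need not favour the drug.

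This is a cheap improvement to descriptive reporting. It does not threaten any inferential result.

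**What to change.** Keep the Table 1 windows. Add one row, end of treatment (last on-treatment value), to each Part 2 laboratory, vital-sign, eGFR, ECG and 6MWD table. Draw it from all visits whatever the study day, and show it separately for patients who discontinued and patients who moved to extended access. State how soon after the last dose a value must be taken to count as on treatment; SAP 3.4.5.3 already excludes eGFR values 14 or more days after the last dose. Report the median and range of study day beside the row.

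Optionally, add a worst on-treatment value row for safety parameters, limited to those with a stated direction of concern.

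Widening the windows to meet at midpoints is less attractive. Week 32 would run over Days 197-308 and Week 56 over Days 309-476. No day would be uncovered, but values up to 84 days off target (308 - 224 = 84) would carry a visit label, and the planned by-visit results would change.

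The cost is a few descriptive rows from data already collected, which mix different treatment durations; the by-visit results stay as planned. Separately, the statements on Part 2 escalation in Protocol 7.1 and 7.3 must be reconciled before anyone can say whether off-grid post-escalation checks in Cohorts 1 and 2 need similar handling.

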### 3.7.4 Analysis Windows for Unscheduled and End of Treatment Visits (Part 1)

Additionally, unscheduled assessments and end of treatment assessments will be used in efficacy and safety analyses if the unscheduled assessment was collected within the scheduled window below. Study day will be calculated for each unscheduled assessment and compared to the protocol defined study day for each visit. In general, analysis windows for unscheduled and end of treatment visits in Part 1 will be defined as follows:

**Table 2. Visit Windows for Unscheduled and End of Treatment Visits in Part 1**

Analysis Visit	Study Day	Analysis Window
Day 1	1	$\text{Study Day} \leq 1$
Week 1	7	$2 \leq \text{Study Day} \leq 10$
Week 2	14	$11 \leq \text{Study Day} \leq 20$
Week 4	28	$21 \leq \text{Study Day} \leq 42$
Week 8	56	$43 \leq \text{Study Day} \leq 70$
Week 12	84	$71 \leq \text{Study Day} \leq 98$
Week 16	112	$99 \leq \text{Study Day} \leq 119$

Records from unscheduled or end of treatment visits that do not fall within an analysis window will be listed, but will not be analyzed. Per Section 3.4.4, for the 6MWT analysis, if use of the visit windows yields more than one value for a particular visit, the average of the two or more values will be used for analysis. For all other analyses, including the eGFR and safety analyses, the value closest to the target study day should be used (Table 2).

## 5. APPENDICES

### 5.1 Appendix A: Ambulatory Blood Pressure Monitoring (ABPM)

Throughout this section, “ambulatory blood pressure” refers to the systolic and diastolic pressures, pulse pressure, and heart rate as collected via 24-hour ABPM. If multiple 24-hour APBM collections occur for a nominal study visit, the last 24-hour APBM collection will be used in the analysis.

Three ambulatory blood pressure parameters will be calculated for each patient using the 24-hour ABPM data.

1. A patient’s mean 24-hour ambulatory blood pressure is calculated as the average of all valid measurements taken from the patient’s ambulatory blood pressure monitoring device.
2. A patient’s mean daytime ambulatory blood pressure is calculated as the average of all valid measurements taken from 6 am to 10 pm.
3. A patient’s mean nighttime ambulatory blood pressure is calculated as the average of all valid measurements taken from 10 pm to 6 am next day.

For a given 24-hour period average, the numerator is the sum of all valid ambulatory blood pressure measurements, while the denominator is the number of all valid blood pressure measurements.

Using each of the three ambulatory blood pressure parameters (24-hour, daytime, nighttime) calculated for each patient, actual values and change from baseline values will be summarized descriptively by received study drug at all scheduled study visits for all four ambulatory blood pressure assessments (systolic blood pressure, diastolic blood pressure, pulse pressure, heart rate). Descriptive summaries will include confidence intervals for each treatment group as well as the difference between the treatment group’s means. Additionally, blood pressure analyses described in Section 5.1 will be performed using the ABPM measurements.

## **5.2 Appendix B: Listing of Tables Included for Part 2 Analysis**

A subset of TLFs in Part 1 will be used in Part 2. Minor modifications are anticipated due to the combined dose levels (BARD vs PBO-BARD). All TLFs in Part 2 will only include data associated with Part 2 of the study. No cumulative summaries or listings will be provided.

Efficacy summaries that include a change from baseline will summarize both change from original baseline as well as change from Week 16. No inferential statistics will be provided for Part 2 data.

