5.1.2. Fluid Overload

Similar to ERAs in certain patient populations, including bosentan in advanced congestive heart failure and avosentan in advanced CKD, bardoxolone methyl treatment was found to be associated with an increased risk for fluid overload and heart failure hospitalizations in the BEACON trial, which enrolled patients with Stage 4 CKD (eGFR 15-29 mL/min/1.73 m²) and type 2 diabetes. The overall increased risk for fluid overload and heart failure events with bardoxolone methyl appeared to be limited to the first three to four weeks after initiation of treatment. Elevated BNP and prior hospitalization for heart failure were identified as risk factors that contributed to increased risk for these events. The increased risk for these events from bardoxolone methyl treatment had not been observed in six previous CKD studies, which were mostly conducted in patients with Stage 3b CKD (eGFR 30-44 mL/min/1.73 m²), patients with hepatic dysfunction, cancer patients, or healthy volunteers.

Review of admission notes and narrative descriptions for heart failure hospitalizations in BEACON indicates that heart failure in bardoxolone methyl-treated patients was often preceded by rapid fluid weight gain (several kilograms within the first weeks of treatment initiation) and was not associated with acute renal decompensation or acutely reduced left ventricular contractility. Available data from BEACON and other studies suggest that bardoxolone methyl treatment can differentially affect hemodynamic status according to the clinical condition of patients and likely promotes fluid retention in patients with more advanced renal dysfunction and other recognized risk factors associated with heart failure at baseline. This current study will employ risk mitigation procedures to reduce the potential for bardoxolone methyl-induced fluid overload, including exclusion of patients with the identified risk factors and close monitoring for fluid retention within the first month of treatment.

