### 3.3 Analysis of Treatment Group Comparability

Demographic information (age, sex, ethnicity, race), baseline characteristics (baseline BMI, weight) and baseline disease characteristics (including PAH classification and details, time since diagnosis, baseline PAH concomitant medications, thromboembolic disease assessment, pulmonary function testing, oxygen use during 6MWTs and available baseline right heart catheterization data) will be summarized by treatment arm for all randomized patients.

Descriptive baseline summaries of continuous data will present the group mean, standard deviation, median, minima, and maxima. Descriptive summaries of discrete data will present the category counts as frequencies and percentages.

Unless otherwise stated, the baseline value of any variable will be defined as the last available value recorded prior to the first administration of bardoxolone methyl/placebo. Missing values will not be imputed, unless otherwise noted, and will be tabulated as missing.

### 3.4 Analysis of Part 1

Part 1 data will be analyzed using the analysis populations defined in [Section 3.1](#). Separate analyses will be performed by each cohort. Part 1 analyses will only include data from the placebo controlled portion of the study. If a subject does not complete Part 1, or chooses not to enter Part 2, then all their data will be used in Part 1. If a subject enters Part 2, then all data up to and including the Week 16 visit will be included in Part 1.

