### 3.4.5.7 ECG

Actual values for the 12-lead ECGs collected at each visit and changes from baseline in ECG measures (i.e., RR, PR, QRS, QT/QTc interval) at post-baseline visits will be summarized. Additionally, frequency counts for ECG results (normal, abnormal not clinically significant, abnormal clinically significant, or unable to evaluate) will be summarized at each visit. If the scheduled assessment is missing, use the recheck measurement closest in time to scheduled visit (if available).

## 3.5 Analysis of Part 2

All patients in Part 2 will receive an active dose of bardoxolone methyl. Patients must be compliant with dosing and complete Part 1 according to the protocol to be eligible for continuation into the extension period (Part 2). Therefore, separate populations for safety and efficacy will not be defined for Part 2 analyses.

The Part 2 safety and efficacy analyses will be summarized by randomized treatment, pooling all placebo patients and all active patients into various subgroups:

- All PAH patients (Cohorts 1, 2, 3a, and 3b patients)
- All CTD-PAH patients (CTD-PAH patients in Cohorts 1, 2, and 3a)
- All Non-CTD PAH patients (Non-CTD PAH patients in Cohorts 1, 2, and 3b)
- All PH patients (Cohorts 4a, 4b, 4c, 4d)

Due to the ongoing nature of this study, summary of Part 2 data will be strictly by patients initially randomized to active versus placebo patients that transition to active therapy. The groups will be labeled as BARD or PBO-BARD. All patients randomized to an active dose of bardoxolone methyl in Part 1 will be summarized with the BARD group in Part 2 analyses. All patients randomized to placebo in Part 1 will be summarized with the PBO-BARD group in Part 2 analyses.

Additional by-dose level results may be presented to explore long term trends by dose level, but will be included in an ad hoc manner.

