### 3.5.5 Safety

Safety analyses described in Section 3.4.4 will be performed on available safety data from Part 2 using the Part 2 treatment groups (BARD, PBO-BARD). Change from baseline summaries of safety described in 3.4.3 will include both change from baseline (Part 1) and change from the end of Part 1 (Week 16) for Part 2.

Analyses of adverse events will count only Part 2 treatment-emergent adverse events (TEAEs), defined as new or worsened events after the Week 16 visit. New or worsened events after Week 16 visit are those events with an AE start date after the Week 16 study visit, or previously recorded AEs with an adverse change in severity (e.g., went from mild to moderate or moderate to serious) after the Week 16 study visit. Similarly, only new onset concomitant medications (date of first dose after the Week 16 visit) will be included in Part 2 summaries.

Shift tables will be provided to assess changes from normal to abnormal shifts from Week 16 to each nominal visit for chemistry and hematology parameters.

Additional details will be provided in the mock Tables, Listings, and Figures.

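### The SAP plans no integrated adverse-event summary timed from first bardoxolone dose, and its Part 2 BARD and PBO-BARD columns are not like for like

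*SAP*

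**What the plan says.** SAP Section 3.4 fixes the scope of Part 1: "Part 1 analyses will only include data from the placebo controlled portion of the study". Section 3.4.5.1 drops Part 1 AEs with onset after the Week 16 visit date. Section 3.5.5 counts in Part 2 only AEs that are new or worse after that visit. Appendix B (5.2) completes the split: "All TLFs in Part 2 will only include data associated with Part 2 of the study", and "No cumulative summaries or listings will be provided".

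Section 3.5 defines the columns: "The groups will be labeled as BARD or PBO-BARD", and "All patients randomized to placebo in Part 1 will be summarized with the PBO-BARD group in Part 2 analyses". It also limits who is in them: "Patients must be compliant with dosing and complete Part 1 according to the protocol to be eligible for continuation".

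Section 3.4.5 exempts AEs from by-visit summary. Section 3.4.5.1 counts each patient once per system organ class and preferred term. Neither section divides AEs by time on drug, and neither gives a rate per patient-year.

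On timing, Protocol 5.1.2 reports that in the Stage 4 CKD and type 2 diabetes trial the excess risk of fluid overload and heart failure "appeared to be limited to the first three to four weeks after initiation of treatment". Protocol 9.1.1 requires weight monitoring at entry to the extension as close as after randomisation, because placebo patients are then starting active drug.

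**The concern.** Several known effects of this drug come early. Besides the fluid-overload finding, the protocol describes transaminases peaking about two to four weeks after starting (5.1.3), muscle spasms mostly in the first two months (5.1.4) and a fall in magnesium within four weeks (5.1.6). The natural time axis for safety is time since first bardoxolone dose.

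The SAP uses calendar part instead. For patients randomised to bardoxolone, the early weeks lie in Part 1 tables. For crossovers they lie in the Part 2 PBO-BARD column, in the same count as an extension that continues beyond Week 32 until extended access opens (Protocol 7.1). Two things are at stake. Information on early AEs from a sizeable share of drug starts is not brought together. And a reader of the Part 2 tables may take a BARD versus PBO-BARD difference for something other than time on drug. The dose-range recommendation rests on the totality of data, including acceptable safety (SAP 1.5.2), so both affect how the evidence is read.

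**Working it through.** **1. Where each starter's early AEs appear**

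| Group | First 4 weeks on drug | Table holding those AEs | Also in the same count |
|---|---|---|---|
| Randomised to bardoxolone | Day 1 to Week 4 | Part 1 active | Rest of Part 1, to Week 16 |
| Placebo crossover | Weeks 16 to 20 | Part 2 PBO-BARD | All later extension follow-up |

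The Part 2 BARD column holds no early weeks. Its patients completed 16 weeks on drug.

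**2. Number of starters** (Protocol 7.2 for cohort sizes, 7.3 for allocation)

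- Planned total: 38 + 16 + 6 × 24 = 198. Maximum: 38 + 16 + 6 × 72 = 486. Both match the protocol.
- Expected planned active: 54 × 0.75 + 144 × 2/3 = 40.5 + 96 = 136.5. Placebo: 13.5 + 48 = 61.5.
- The readable text gives no Part 1 dropout rate. Assume 80-100% of placebo patients cross over: 0.8 × 61.5 = 49.2, up to 61.5.
- All starters: 136.5 + 49.2 = 185.7, up to 198.
- Crossover share: 49.2/185.7 = 26%, up to 61.5/198 = 31%.
- At maximum enrolment: 328.5 active and 157.5 placebo, giving 454.5 to 486 starters.

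**3. Precision gained by combining** (treats the two starter groups as exchangeable)

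- Zero-event one-sided 95% upper bound, 1 − 0.05^(1/n): 2.2% at 136.5, 1.6% at 185.7, 1.5% at 198. At maximum enrolment it goes from 0.91% to 0.61-0.66%.
- Half-width at a 10% event rate, 1.96 × √(0.1 × 0.9/n): 5.0 points at 136.5, and 4.2-4.3 points at 185.7-198.
- Relative width: √(136.5/185.7) = 0.86 and √(136.5/198) = 0.83, so intervals are 14-17% narrower.

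**4. Illustration of the column contrast** (assumed rates, identical drug effect in everyone)

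Take a risk h in the first 4 weeks on drug and 1% per 4 weeks afterwards. Over Weeks 16 to 32:

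- BARD: 1 − 0.99^4 = 3.9%.
- PBO-BARD: 1 − (1 − h) × 0.99^3, which is 6.9% for h = 4% and 12.7% for h = 10%.

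The gap comes only from time on drug.

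**5. Illustration of unequal follow-up** (assumed durations)

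Allocation is 3:1 in Cohorts 1-2 and 2:1 in Cohort 3, so pooled PAH columns mix cohorts in different proportions. With 104 weeks of follow-up in Cohorts 1-2 and 32 in Cohort 3:

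- BARD mean: (40.5 × 104 + 32 × 32)/72.5 = 72.2 weeks.
- PBO-BARD mean: (13.5 × 104 + 16 × 32)/29.5 = 64.9 weeks, so BARD is 11% longer.
- With 16 weeks in Cohort 3: 65.2 against 56.3, or 16% longer.

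**6. The Week 16 date**

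Protocol 7.1 makes the Week 16 visit Day 1 of the extension. An AE with onset on that date stays in Part 1 under SAP 3.4.5.1 and is not counted in Part 2 under 3.5.5. An event on a crossover's first bardoxolone day is then tabulated under placebo.

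**7. Other text that does not fit the ban**

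SAP 3.5.2 summarises total time in study from first dose. SAP 3.5.3 covers medications started in Part 1 or Part 2. SAP 2.3 promises by-patient listings of all collected data.

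**The case against.** A reader might infer that crossovers are left out of the safety evaluation, or that nothing is timed from their first dose. The documents do not support either reading. The Part 1 safety population includes everyone dispensed drug, early dropouts too (SAP 3.1.4). PBO-BARD begins where crossovers start bardoxolone. Apart from the Week 16 date, the two sets of tables together cover all starters. Chemistry (including ALT, AST and magnesium) and weight are summarised by visit, with change from Week 16 (SAP 3.4.5.2, 3.4.5.5, 3.5.5). The Part 2 windows give results at Weeks 18 and 20, and at Weeks 22 and 24 for Cohorts 3 and 4. Crossover eGFR is re-baselined at Week 16. BNP is collected at the same visits, and any analysis of it may lie in redacted text. All of this stands and confines the point mainly to AEs and SAEs.

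Nor is BARD versus PBO-BARD a planned comparison: the columns are labelled by prior treatment and carry no inferential statistics. The stated safety objective is 16 weeks of drug against 16 weeks of placebo, which Part 1 serves. The fluid-overload statement comes from one Stage 4 CKD trial. The protocol says six earlier CKD studies did not show that risk, and this trial excludes patients with the identified risk factors.

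Combining starters has limits. Crossovers are selected completers without concurrent placebo. In Cohorts 3 and 4 their up-titration is optional at Week 20, whereas Part 1 patients escalate at Week 4 unless a DLT is reported. The combined column would not by itself identify a tolerable dose. On the other side, those crossovers begin at the same 5 mg as Part 1 starters, and original assignment stays blinded through Week 20, so a first-four-weeks comparison is reasonable. The mock tables cited in SAP 3.5.5 are not in the documents and could add detail.

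**Conclusion.** The point holds in a limited form. No AE or SAE summary runs from first bardoxolone dose across all starters. Crossovers' early AEs are not separated from later follow-up. The Part 2 columns differ in prior exposure and in selection for tolerating 16 weeks of drug. Several SAP sections together produce this, so deleting the Appendix B sentence alone would not cure it.

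The affected group is about 26-31% of planned starters. The gain from combining is a zero-event bound of 1.5-1.6% in place of 2.2%. Both figures assume 80-100% crossover, and the bound also assumes exchangeable starter groups. The contrasts of 3.9% against 6.9-12.7%, and of 11-16% in follow-up, rest on assumed rates and durations and only show the direction of the distortion. In a descriptive Phase 2 extension this is an inexpensive improvement that should be made. It does not invalidate the Part 1 safety comparison.

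**What to change.** - Remove or qualify the Appendix B sentence, and reconcile it with SAP 2.3, 3.5.2 and 3.5.3.
- Add to SAP 3.5.5 a descriptive TEAE/SAE table on a clock starting at first bardoxolone dose: Day 1 for BARD, Week 16 for PBO-BARD. Report the first 4 weeks, the first 16 weeks and later, with patients at risk and events per patient-year. Show the two starter groups separately and combined, by cohort or SAP pooling group, with Part 1 placebo alongside.
- Assign to bardoxolone any AE that starts on the Week 16 visit date after a crossover's first bardoxolone dose. Where onset time is not recorded, state a fixed rule.
- State that the combined column is descriptive, because crossovers are selected Part 1 completers without concurrent placebo and their titration timing differs.

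The cost is SAP wording and a few tables from data already collected. The main downside is that the combined column could be over-read, which the last item addresses.
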